## 5.2. Screening, Randomization, Masking Procedures, Study Visits

## 5.2.1. Initial and Continuing Informed Consent

Informed consent is the process of ensuring that study participants fully understand the purpose of the study and what will and may happen to them while participating in a research study. Initial written informed consent is required before performance of any study-related procedures. The informed consent process continues throughout the study. Key study concepts are reviewed with the participant at designated times and as needed, and the review is documented.

Additionally, if any new information becomes available that, in the judgment of the Sponsor and/or PI, may affect the participant's decision to continue in the trial, such information will be shared with the study participant and may be the basis for requiring a new consent form to be signed.

A copy of the signed informed consent form (ICF) will be provided to the participant and the original ICF will be filed with the participant's study record.

Page **41** of **106** 

## 5.2.2. Screening, Visit 1 (Day -28 to -1)

Once informed consent has been obtained the participant will be considered enrolled in the trial. The following procedures will be completed during screening to determine study eligibility and may occur over multiple screening visits. Additional screening visits may be scheduled for any follow up as needed, but are not required. At the screening visit(s), the PI or designee will provide prospective volunteers with a detailed description of the study objectives and study participation requirements, as well as potential health risks and benefits associated with study participation. Baseline data are obtained during screening, which may occur over the course of several contacts/visits, between 28 days prior to and on Day 1, the day of vaccination. All inclusion/exclusion criteria must be assessed from data obtained within that period, unless otherwise specified in the eligibility criteria. After study information has been provided and the appropriate informed consent has been obtained, the following procedures are performed by PI/designee:

- a) Confirms that written informed consent has been given and solicits and discusses any remaining questions the participant may have;
- b) Assign screening number once study specific consent form has been signed;
- c) Obtain demographic and contact (e.g., address, telephone, email) information;
- d) Obtain medical history; including history of any vaccination in the last 30 days and ever received vaccination against *Neisseria meningitidis*, tetanus or diphtheria containing vaccines
- e) Obtain history of medication use in the past 30 days;
- f) Measure height & weight;
- g) Perform full physical exam, including vital signs (blood pressure, pulse and temperature section 5.5.1); and
- h) Collect blood samples (18 mL) for screening laboratory testing: hematology (hemoglobin, platelet count and WBC), clinical chemistry (creatinine, albumin, ALT and total bilirubin), serum HCG pregnancy test (females of childbearing potential only) and screening for HIV, HCV and HBV (Appendix I).

#### 5.2.3. Randomization

Enrollment will be performed online using the enrollment module of AdvantageEDCSM, the Emmes Corporation's electronic data capture (EDC) system. Randomization will occur on the day participants are to receive their first study vaccination, after confirmation of eligibility and immediately prior to vaccination.

Participants will be assigned to a coded treatment assignment after demographic and eligibility data have been entered into the system. The unblinded pharmacist will be provided with the treatment assignment codes for preparation of the vaccine to be given to each participant. The research pharmacist will maintain the treatment code list in a secure place.

Page **42** of **106** 

Based on this randomization schedule each participant will be assigned to one of the following three treatment groups:

Group	Vaccine
1	Adjuvanted Study vaccine (MCV-5)
2	Non-adjuvanted Study vaccine (MCV-5)
3	Reference vaccine (Menactra®, ACYW)

#### 5.2.4. Vaccination, Visit 2 (Day 1)

#### **Prior to Vaccine Administration**

- a) Obtain interim medical and medications history to confirm continued eligibility;
- b) Measure vital signs;
- c) Perform targeted physical exam based on complaints, interval history and to confirm absence of abnormality at the injection site (deltoid);
- d) For female participants of child bearing potential, perform urine or serum pregnancy test;
- e) Obtain blood samples (20 mL) for immunological testing; and
- f) Record randomization code for eligible participant

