## 4.3. Eligibility

#### 4.3.1. Inclusion Criteria

Male and female participants will be eligible for inclusion if ALL of the following apply at the time of screening:

- 1. Age 18 to 45 years of age inclusive
- 2. Written informed consent of volunteers
- 3. Healthy as established by medical history, laboratory evaluation and screening evaluations including clinical physical examination
- 4. Participants must have the following laboratory parameters:
  - a. Hemoglobin: ≥ 10.5 g/dL for female, ≥ 11.0 g/dL for male
  - b. White cell count: 3,300 to 12,000 cells/ mm3
  - c. Platelets: 125,000 to 550,000/ mm3
  - d. ALT < 1.25 times the institutional upper limit of normal (ULN)
  - e. Creatinine and total bilirubin ≤ institutional ULN
  - f. Albumin ≥ institutional lower limit of normal
- 5. Participants are able to understand and comply with planned study procedures and be available for all study visits
- 6. Female subjects must be of non-childbearing potential (defined as surgically sterile or postmenopausal for more than 1 year), or if of childbearing potential must be practicing abstinence or using an effective licensed method of birth control (e.g., history of hysterectomy or tubal ligation; use hormonal or barrier birth control such as implants, injectables, combined oral contraceptives, some intrauterine devices (IUDs), cervical sponges, diaphragms, condoms with spermicidal agents; or must have a vasectomized partner) within one month of vaccination and must agree to continue such precautions for 84 days after vaccination. A woman is eligible if she is monogamous with a vasectomized male.

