# 4.3.2. Exclusion Criteria

Study Protocol: ACYWX-001/VAC 046

Participants with any of the following criteria at study entry will not be eligible for participation:

- 1. Previous vaccination against Neisseria meningitidis.
- 2. Known exposure to *Neisseria meningitidis* in the past.
- 3. History of meningitis or seizures or any neurological or psychiatric disorder.
- 4. Administration of any other vaccine within 30 days prior or after administration of study vaccines.
- 5. Use of any investigational or non-registered drug or vaccine within 30 days prior to the administration of study vaccines or planned during the study.
- 6. History of allergic disease or known hypersensitivity to any component of the three study vaccines.
- 7. History of Serious Adverse Reactions following administration of Tetanus Toxoid, Diphtheria Toxoid or CRM containing vaccines.
- 8. History of Guillain-Barré syndrome.
- 9. Confirmed or suspected immunosuppressive or immune-deficient condition.
- 10. A family history of congenital or hereditary immunodeficiency.
- 11. Chronic administration (defined as more than 14 days) of immune-suppressants or other immune-modifying agents within six months prior to administration of study vaccine. (For corticosteroids, this means prednisone, or equivalent, > 0.5 mg/kg/day; topical or inhalable steroids are allowed.)
- 12. Laboratory confirmed infection of either hepatitis B virus (HBs Ag positive on ELISA), hepatitis C virus (anti-HCV positive on ELISA as well as PCR) or human immunodeficiency virus (HIV on ELISA).
- 13. Major congenital defects or serious chronic illness.
- 14. Acute or chronic, clinically significant pulmonary, cardiovascular, hepatic, or renal functional abnormality, as determined by medical history, physical examination or laboratory screening tests.
- 15. Known bleeding disorders.
- 16. Administration of immunoglobulins and/or any blood products within the three months preceding the administration of study vaccines or planned administration during the vaccine period.
- 17. History (within the past year) or signs of alcohol or substance abuse.
- 18. Pregnancy or lactation. A negative pregnancy test will be required before vaccination for all women of childbearing potential.
- 19. A Body Mass Index (BMI) above 30.

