#### Post Dose - Observation Period

- a) Participants will remain at the site for at least 60 minutes post-vaccination.
- b) After 60 minutes study staff will assess and record oral temperature, systemic (headache, fatigue/malaise, myalgia, arthralgia, diarrhea and anorexia) and local injection site (pain, redness/erythema, swelling/induration) reactions.
- c) The PI (or designee) may determine that a participant requires further on-site observation; or clinical assessments as needed.
- d) When all study related procedures are complete and the PI (or designee) determines that a participant's condition is acceptable, the participant will be discharged from study site.
- e) Before discharge, the participant will be provided with supplies including a thermometer, injection site measuring device, and a Memory Aid; instructed in their use; and provided with written materials, follow-up visit information, and contact telephone numbers for study staff.

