## 7.4. Sample Size Justification

Since this study is a Phase 1 trial it is designed to provide preliminary safety and immunogenicity data that may support testing the study product in additional larger cohorts in adults and in age-descending studies.

With 20 vaccine recipients per vaccine group, this study's design allows a greater than 90% chance of observing an AE that has an 11% chance of occurrence. Conversely, if no AEs are observed in 20 vaccine recipients, the study will be able to rule out AEs occurring at a rate of approximately 14% based on the upper bounds of the one-sided 95% Confidence Interval.

No formal statistical hypothesis testing is planned for this first time in human Phase 1 study whose objectives are aimed to descriptively evaluate the safety and immunogenicity profile of the study vaccines

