## 9.2. Study Pause Rule

The following study pause rules will automatically pause or halt further vaccinations. However participants already enrolled will continued to be followed for safety during the pause. These pause rules refer to suspected adverse reactions and will be triggered automatically if any of the event described below are met during the conduct of the study:

- One or more participants experience a serious adverse reaction.
- One or more participants experience a Grade 4 injection site reaction.
- Two or more participants experience the same Grade 3 injection site reaction.
- Two or more participants with the same severe (Grade 3) systemic reactogenicity signs or symptoms, within seven days following vaccination.
- Two or more participants experience the same vaccine-related Grade 3 or higher clinical (including fever) or laboratory abnormality.

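### Subjective solicited symptoms are not graded before the Day 1 injection, and the SAP has no new-or-worse rule for them, so symptoms that precede the dose may be tabulated as reactions

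*Protocol*

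**What the plan says.** **Before the dose.** Protocol 5.2.4 lists these steps for Visit 2: "Obtain interim medical and medications history to confirm continued eligibility", vital signs, and "Perform targeted physical exam based on complaints, interval history and to confirm absence of abnormality at the injection site (deltoid"). Section 5.5.1 includes oral temperature among the vital signs. Section 5.5.4 says the interim history asks about changes, including signs and symptoms, but sets no checklist and no grade.

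**After the dose.** The first structured record is in the observation period of 5.2.4: "After 60 minutes study staff will assess and record oral temperature, systemic (headache, fatigue/malaise, myalgia, arthralgia, diarrhea and anorexia") and local reactions. Daily self-assessment follows with the Memory Aid.

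**Eligibility.** Section 4.3.1 opens: "Male and female participants will be eligible for inclusion if ALL of the following apply at the time of screening". The nearest exclusion on acute disease is item 14 of 4.3.2: "Acute or chronic, clinically significant pulmonary, cardiovascular, hepatic, or renal functional abnormality". Item 20 lets the investigator exclude for any other condition. None of the 6 inclusion and 20 exclusion criteria names fever, acute illness or an abnormal injection site.

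**Analysis.** SAP 3.3 defines the baseline value as the last one before vaccination. SAP 9.4 instead treats a condition present at screening as baseline, and then includes all reported events in the summaries. SAP 9.4.2 tabulates solicited events from 60 minutes onward. The columns of Table 14.3.1.4 run from 60 minutes to Day 8, and Table 14.3.1.1 has a row for solicited events within 60 minutes.

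**The concern.** Solicited reactions within seven days are the first primary endpoint. The study is descriptive, so the absolute rates in each arm are its result. Protocol 13.2 expects the MCV-5 rates to be consistent with published Menactra rates, several of which concern non-specific complaints: headache 41.4%, fatigue 34.7%, arthralgia 19.8%.

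These complaints also occur without vaccination. A participant who arrives with a headache and still has it an hour later would be graded at 60 minutes, with no pre-dose grade to set against it. If it lasts into the evening it can also enter the Day 1 diary entry.

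Little downstream would filter it out. Under Protocol 8.1, solicited events stay on their own form unless serious. The endpoint lists in Protocol 7.3.1 and SAP 9.4.1 break down unsolicited events by relatedness, but not solicited ones. A grade that was never taken cannot be recovered at analysis.

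**Working it through.** **1. The plan's own figures.** Protocol 7.4 says that 20 per group "allows a greater than 90% chance of observing an AE that has an 11% chance of occurrence": 1 − 0.89^20 = 0.903. It also says that with no events the study can "rule out AEs occurring at a rate of approximately 14% based on the upper bounds of the one-sided 95"% limit: 1 − 0.05^(1/20) = 0.139. Both reproduce, and neither calculation uses the Day 1 checks.

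**2. Which baseline applies to which symptom.**

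| Onset of symptom | SAP 9.4 (screening) | SAP 3.3 (last value before dose) |
|---|---|---|
| Before or at screening, unchanged | pre-existing | pre-existing, if a value was recorded |
| Between screening and injection | not covered | pre-existing, if a value was recorded |
| After injection | event | event |

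The middle row is the gap. The two sections disagree, and for subjective symptoms SAP 3.3 has no graded value to use.

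**3. Effect of one participant.** 1/20 = 5 percentage points. This is a maximum for each symptom, because it is zero if that participant would have reported the symptom after vaccination anyway.

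**4. Expected effect.** Let b be the share of participants with a given symptom just before the dose, and p the true post-dose rate, taken as independent. If every pre-dose symptom were counted, the observed rate would be p + b(1 − p). The documents give no value for b; 1% to 10% is assumed.

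| b | At least one in an arm of 20: 1 − (1 − b)^20 | Expected in 60: 60b |
|---|---|---|
| 1% | 18% | 0.6 |
| 2% | 33% | 1.2 |
| 5% | 64% | 3.0 |
| 10% | 88% | 6.0 |

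At b = 5%:
- Headache: 0.414 + 0.05 × 0.586 = 0.443.
- Arthralgia: 0.198 + 0.05 × 0.802 = 0.238.

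**5. Between-arm comparison.** Allocation is randomised, so b is expected to be equal across arms. Exact enumeration of the two-sided Fisher test at the 5% level, with 20 per arm and equal rates, was run at the headache and arthralgia rates above. It gives a rejection probability of 2.1% to 2.4% for b from 0 to 10%. The screening comparison with Menactra does not produce more false signals.

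**The case against.** A reader might infer that a febrile or ill volunteer is eligible on Day 1, that no pre-dose record exists, and that the symptoms will be counted as vaccine reactions. The documents do not support that reading.

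- **Records exist.** Temperature is measured before the dose and appears in SAP Listing 16.2.9.1. The history asks about symptoms and the deltoid is inspected. Pre-existing fever and visible local signs can be identified afterwards. The gap concerns the grade of subjective symptoms.
- **Eligibility is re-confirmed.** Protocol 5.2.2 accepts eligibility data up to Day 1, 5.2.3 randomises after confirmation of eligibility, Appendix I marks the criteria at Visit 2, and exclusions apply at study entry. Item 20 is available. No explicit criterion names acute illness, but that leaves the matter to investigator judgement; it does not make an ill volunteer eligible.
- **Onset wording.** Protocol 8.1 describes a solicited symptom as one that started after vaccination, and 8.3.1 defines an adverse event the same way. SAP 9.4 defines treatment-emergent events as arising after baseline or worsening. So such symptoms *may* be counted; the plan does not say that they are.
- **Pause rules.** Protocol 9.2 limits them to suspected adverse reactions, and one reads "Two or more participants experience the same vaccine-related Grade 3 or higher clinical (including fever) or laboratory abnormality". Ordinary pre-dose headache or fatigue is unlikely to trigger them.

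All four points stand. What survives is that the onset principle has no graded pre-dose observation behind it for subjective symptoms, is anchored to screening in SAP 9.4, and is not carried into SAP 9.4.2.

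**Conclusion.** The concern holds in a limited form. The plan does not say how a subjective solicited symptom that begins between screening and injection is to be graded before the dose or tabulated after it, and the SAP's two baseline definitions give different answers. The consequence is possible inflation of absolute reactogenicity rates in a primary endpoint. It is at most 5 percentage points per affected participant in an arm of 20. At an assumed 5% pre-dose prevalence it is about 3 points for headache (44.3% − 41.4% = 2.9) and 4 for arthralgia (23.8% − 19.8% = 4.0).

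These sizes rest on an assumed prevalence and on every pre-dose symptom being counted, so they are upper illustrations. No between-arm bias is expected, and the sample-size statements are unaffected. The change is worth making because it is cheap and the missing observation cannot be reconstructed.

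**What to change.** 1. **Protocol 5.2.4.** At Visit 2, before injection, grade the solicited symptoms on the form used at 60 minutes. Use the full list in 5.5.6, since the 60-minute list in 5.2.4 does not name chills or vomiting.
2. **SAP Table 14.3.1.4.** Add a pre-dose column.
3. **SAP 9.4.2.** State that solicited reactions are also tabulated counting only those that are new or of higher grade than before the dose. Keep the all-reported tabulation beside it.
4. **SAP 9.4.** Replace the reference to when the participant is *screened* with the pre-vaccination baseline of SAP 3.3.

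The cost is one short checklist at an existing visit, one table column and two SAP sentences. Rates in the new-or-worse tabulation may be slightly lower than in the all-reported one.

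Separately, the sponsor should reconcile the Visit 2 checks, which are made to confirm eligibility, with section 4.3, which names no criterion for acute illness, fever or injection-site abnormality. Whether such a rule is needed, and what it should contain, is for the sponsor and the investigator; none is proposed here.

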#### **Vaccine Administration**

- a) The prospective injection site will be cleaned with an alcohol swab and allowed to dry completely. The study injection will be administered into the deltoid by inserting the needle (25 gauge, 25 mm) into muscle at 90°, holding the muscle mass stable with the noninjecting hand, and slowly depressing the plunger. The needle is removed and the injection site gently rubbed with gauze.
- b) An unblinded clinical staff not involved with clinical assessment will administer the assigned vaccine to the participant.
- c) Document on the CRF as to timing and location of vaccine administration.

#### Post Dose - Observation Period

- a) Participants will remain at the site for at least 60 minutes post-vaccination.
- b) After 60 minutes study staff will assess and record oral temperature, systemic (headache, fatigue/malaise, myalgia, arthralgia, diarrhea and anorexia) and local injection site (pain, redness/erythema, swelling/induration) reactions.
- c) The PI (or designee) may determine that a participant requires further on-site observation; or clinical assessments as needed.
- d) When all study related procedures are complete and the PI (or designee) determines that a participant's condition is acceptable, the participant will be discharged from study site.
- e) Before discharge, the participant will be provided with supplies including a thermometer, injection site measuring device, and a Memory Aid; instructed in their use; and provided with written materials, follow-up visit information, and contact telephone numbers for study staff.

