#### **Endpoints:**

Summaries by product received including the number and percentage of participants experiencing:

- immediate AEs within 60 minutes post-vaccination;
- solicited local or systemic post vaccination reactogenicity reactions within seven days following vaccination (Days one through seven);
- any SAE within six months following vaccination;
- any AE within 28 days following vaccination;
- any Grade 2 or greater solicited local or systemic post vaccination reactions within seven days following vaccination;
- any Grade 2 or greater unsolicited AE within 28 days following vaccination;
- any unsolicited AE within 28 days following vaccination judged to be related to study product; and
- any Grade 2 or greater unsolicited AE within 28 days following vaccination judged to be related to study product.

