#### 9.4.2 Solicited Events and Symptoms

Systemic and local solicited adverse events were collected 60 minutes post-vaccination and then daily for 7 days after vaccination and graded on a scale of 0 (absent), 1 (mild), 2 (moderate) and 3 (severe). Systemic events include: elevated oral temperature, headache, fatigue/malaise, joint pain/arthralgia,

muscle pain/myalgia, diarrhea, anorexia, chills and vomiting. Local events include: pain at injection site, erythema at injection site, and swelling at injection site.

The proportion of participants, within each treatment arm, reporting at least one solicited adverse event will be summarized for each solicited adverse event, any systemic symptom, any local symptom, and any symptoms. The 95% CI calculated using Clopper-Pearson methodology from a binomial distribution (SAS PROC FREQ with a binomial option) will be presented (Table 14.3.1.2).

For each systemic and local event, any systemic event, any local event, and any solicited event, the maximum severity over 7 days after each vaccination will be summarized for the FA population. The number and percentage of participants reporting each event will be summarized by the maximum severity for each treatment group. For each event the denominator is the number of participants with non-missing data for the specific event (Table 14.3.1.3).

The number and percentage of participants reporting any solicited adverse event, any local symptom, any systemic symptom and for each individual symptom will be summarized for each day post vaccination by Treatment group (Table 14.3.1.4). The percent of participants reporting any systemic solicited event and any local solicited event will be displayed graphically in a bar chart in Figures 14.3.1.5.1 and 14.3.1.5.2, respectively.

Fisher's exact test will be used to compare the proportion of participants with solicited local and systemic reactogenicity events between each of the MCV-5 groups and the Menactra® group. The results will be summarized in Table 14.3.1.6.

The primary purpose of the statistical comparisons is to screen out potential solicited reactogenicity events that need further clinical evaluation. Therefore, they are not considered formal statistical hypothesis tests and it is acknowledged that there will be inflated Type I errors (i.e., inflated false statistical significances) from performing multiple unadjusted comparisons.

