**TABLE 14.3.1.4:** 

Number and Percentage of Participants Experiencing Solicited Events by Severity, at 60 minutes and at Day 1 through Day 8 Post Vaccination by Treatment Group - Full Analysis Population

TABLE 14.3.1.4(a) Any Local or Systemic Symptom

	60 mins (N=X)	Day 1 (N=X)	Day 2 (N=X)	Day 3 (N=X)	Day 4 (N=X)	Day 5 (N=X)	Day 6 (N=X)	Day 7 (N=X)	Day 8 (N=X)
Adjuvanted MCV-5									
N									
None – n (%)									
Mild – n (%)									
Moderate – n (%)									
Severe – n (%)									
Life-Threatening – n (%)									
Not Reported – n (%)									
MCV-5									
N									
None – n (%)									
Mild-n (%)									
Moderate – n (%)									
Severe – n (%)									
Life-Threatening – n (%)									
Not Reported – n (%)									
Menactra®									
N									
None – n (%)									
Mild – n (%)									
Moderate – n (%)									
Severe – n (%)									
Life-Threatening – n (%)									
Not Reported – n (%)									

N = Number of participants in the Full Analysis Population. Severity is the maximum severity reported for each participant for each day.

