**TABLE 14.3.1.4(n) Chills** 

TABLE 14.3.1.4(o) Vomiting

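### The 60-minute symptom check in Protocol 5.2.4 leaves out chills and vomiting, which the SAP treats as solicited and collected at that time point

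*Protocol*

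**What the plan says.** Protocol 5.2.4, under the post-dose observation period, sets the 60-minute assessment: "After 60 minutes study staff will assess and record oral temperature", the systemic symptoms "systemic (headache, fatigue/malaise, myalgia, arthralgia, diarrhea and anorexia", and three local reactions (pain, redness, swelling). Nothing in the wording marks the systemic list as a set of examples.

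Protocol 5.5.6 lists nine solicited systemic items for the seven days after vaccination: fever, headache, fatigue/malaise, arthralgia, myalgia, diarrhea, anorexia, chills and vomiting.

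SAP 9.4.2 states: "Systemic and local solicited adverse events were collected 60 minutes post-vaccination and then daily for 7 days after vaccination". The systemic list that follows ends with "muscle pain/myalgia, diarrhea, anorexia, chills and vomiting", and no symptom is exempted from the 60-minute time point.

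SAP Table 14.3.1.4 is titled to report solicited events "at 60 minutes and at Day 1 through Day 8 Post Vaccination by Treatment Group". Its sub-tables include "TABLE 14.3.1.4(n) Chills" and a matching one for vomiting.

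On the outcome itself, Protocol 7.3.1 lists "immediate AEs within 60 minutes post-vaccination" as its first primary safety summary. SAP 9.4.1 and the first row of Table 14.3.1.1 narrow this to solicited events in the first 60 minutes.

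**The concern.** The SAP plans to report two symptoms at a time point where the protocol does not tell staff to ask about them. Someone following 5.2.4(b) literally would collect 10 of 12 solicited items, yet the SAP describes all 12 as collected.

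Two things are at stake. First, the by-timepoint tables for chills and vomiting may have nothing in the 60-minute column. Second, the SAP's first-hour summary counts solicited events only, so its completeness depends on the list used at that check. This is a first-in-human trial with safety as its primary objective, and immediate reactions head the overall adverse event table.

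**Working it through.** **Symptom lists side by side**

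| Solicited item | Protocol 5.5.6 | 60-minute check, Protocol 5.2.4(b) | SAP 9.4.2, stated as collected at 60 minutes |
|---|---|---|---|
| Fever (oral temperature) | yes | yes | yes |
| Headache | yes | yes | yes |
| Fatigue/malaise | yes | yes | yes |
| Arthralgia | yes | yes | yes |
| Myalgia | yes | yes | yes |
| Diarrhea | yes | yes | yes |
| Anorexia | yes | yes | yes |
| Chills | yes | **no** | yes |
| Vomiting | yes | **no** | yes |
| Pain, redness, swelling (3 local) | yes | yes | yes |

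Systemic coverage at 60 minutes is 7 of 9. Overall coverage is 7 + 3 = 10 of 12.

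**How a gap passes through the tables**

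- Table 14.3.1.4 separates None from Not Reported, so an uncollected symptom can be shown there as missing.
- The Table 14.3.1.1 shell has no such line. Its N is the Full Analysis population, and SAP 9.4 sets the incidence denominator as the total population size. A participant with no recorded immediate solicited symptom is therefore counted as a non-event.
- The Day 1-7 solicited rows of Table 14.3.1.1 carry a footnote excluding the first 60 minutes, so they would not pick up such an event if it is dated to the first hour.
- Protocol 8.1 puts non-serious solicited symptoms on the reactogenicity form, not the AE/SAE form. If chills or vomiting were entered as an unsolicited event instead, they would fall outside the SAP's solicited first-hour row.

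**The plan's own figures**

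The plan gives no first-hour rate. Its only related calculation is in Protocol 7.4, and it reproduces:

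- Chance of at least one event at a rate of 11% in 20 recipients: 1 − 0.89^20 = 0.903, matching the stated figure of more than 90%.
- One-sided 95% upper bound for 0 of 20: 1 − 0.05^(1/20) = 0.139, matching the stated figure of approximately 14%.

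**Size of the possible loss**

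Inputs: seven-day reference-vaccine rates from Protocol 13.2 (chills 9.7%, vomiting 2.3%); 20 per arm, 60 in all. Assumptions: these rates hold in every arm; the two symptoms never occur in the same person, so the rates add to 9.7% + 2.3% = 12.0%; and a share f of these events starts within 60 minutes. The documents do not give f, so a range is shown. The expected number is n × 0.12 × f, and the chance of at least one is 1 − (1 − 0.12f)^n.

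| Assumed f | Expected per arm of 20 | Expected in 60 | Chance of at least one, per arm | Chance of at least one, all 60 |
|---|---|---|---|---|
| 1% | 20 × 0.0012 = 0.024 | 0.072 | 2.4% | 7.0% |
| 5% | 20 × 0.006 = 0.12 | 0.36 | 11.3% | 30.3% |
| 10% | 20 × 0.012 = 0.24 | 0.72 | 21.5% | 51.5% |

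For each f these are upper limits on the change in the first-hour row. The row changes only when the participant had no other immediate solicited symptom and the event was not recorded by another route.

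**The case against.** A reader might infer that the immediate-reaction outcome is in fact undercounted, that the two symptoms are never captured at 60 minutes, or that they will be tabulated as absent. The documents do not support any of these.

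- The synopsis has participants observed for 60 minutes for any immediate reaction or other adverse event, and the Schedule of Events entry is generic. Vomiting in the clinic would be hard to miss. The Memory Aid covers Day 1, and reactions are asked about again at Visit 3.
- The 60-minute form is not in the documents, so it may already include both symptoms.
- The protocol's own wording of the outcome in 7.3.1 takes in immediate events of any kind, so an observed or volunteered episode would count there. The narrowing to solicited events is the SAP's.
- Table 14.3.1.4 has a Not Reported row, so missing cells need not become zeros. Only its sub-table (a) is drawn; the 60-minute columns for chills and vomiting follow from the instruction to continue for each symptom, but are not shown.
- The footnote excluding the first hour is attached to Table 14.3.1.1 only. The shells of Tables 14.3.1.2 and 14.3.1.3 carry no such exclusion, so an early episode noted on the Day 1 Memory Aid could still reach the symptom-level tables and the Fisher comparisons.
- The shorter list may be deliberate. Apart from myalgia, its symptoms match those that Protocol 1.6 calls common (at least 10%) with the reference vaccine, and chills and vomiting fall below that level. The protocol does not give this as a reason.

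These points limit the consequence. They do not remove the mismatch: unprompted capture of two symptoms is not the same as prompted capture of the other ten, and SAP 9.4.2 says that all were collected at 60 minutes.

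**Conclusion.** The inconsistency is real. Under Protocol 5.2.4(b) as written, chills and vomiting are not systematically asked about at 60 minutes, while the SAP says they were collected then and plans to tabulate them. Their 60-minute cells may be empty or Not Reported, and the first-hour solicited row of Table 14.3.1.1 may miss a participant whose only immediate solicited symptom was one of the two.

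The effect is probably very small: at most about a quarter of a participant per arm if no more than 10% of the seven-day events start in the first hour. That rests on the reference-vaccine rates applying to all arms and on an assumed first-hour share. The check is the same in all three arms and the assessors are blinded, so any loss would bear on absolute rates and should not favour one vaccine. This is a minor point of alignment; it does not show that the safety results are biased.

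**What to change.** Add chills and vomiting to the 60-minute assessment in Protocol 5.2.4(b) and, if they are absent from it, to its form, so that the check matches Protocol 5.5.6 and SAP 9.4.2. The cost is one line of protocol and at most two checkboxes on one form.

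If data were already collected without these items, correct the statement in SAP 9.4.2 and footnote Tables 14.3.1.1 and 14.3.1.4(n) and (o) to say that the two symptoms were not solicited at 60 minutes. That costs one sentence and the footnotes.
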